The implementation of the Target Educational Campaign (TEC) will involve Correction Officers working at three jails: the Anna M. Kross Center (AMKC), the Rose M. Singer Center (RMSC), and the Robert N. Davoren Complex (RNDC), all located on Rikers Island in New York City. Correction Officers in these three jails will be approached to complete brief surveys. The study will need 540 completed surveys over the course of the three time points (180 surveys at each). Since identifying information is not being collected from the Correction Officers, it is possible that some of Correction Officers will participate more than once, meaning less than 540 Officers total will participate.

Recruitment Procedures

Recruitment of the study sample will take place in 3 jails on Rikers Island in New York City (NYC): Anna M. Kross Center (AMKC), Rose M. Singer Center (RMSC), and the Robert N. Davoren Complex (RNDC).

How and by whom will subjects be approached and/or recruited?

Correction Officers in these three jails will be exposed to the Targeted Educational Campaign (TEC). Correction Officers will be approached and recruited during roll call and in the staff canteen where they take their meal breaks, or at a time/location agreed upon by the Department of Correction, to complete brief surveys to assess engagement of Target C at three different times: pre-exposure, after 6 months, and after 12 months from the beginning of the TEC. [name] and [name], coordinated and supervised by [name] and [name], will approach Correction Officers briefly presenting the study and asking for completion of the survey.

In the event that social distancing guidelines pertaining COVID-19 prevent the research team for going to the jails to survey the Officers at the 6 and 12-month follow-up time periods, we will coordinate with our study partners to administer the anonymous survey. The Deputy Wardens and/or Captains at the jails will introduce the survey during the daily roll-call meetings, and they will distribute the participant information document and survey to each Officer for their review. The Deputy Wardens and Captains will tell the Officers that the survey is voluntary and anonymous, but if they wish to complete it, they can put their completed survey in a container in the Officer's canteen or other communal space.

Inclusion/Exclusion Criteria

Inclusion Criteria

1. Exposure to the Targeted Educational Campaign
2. Aged at least 21 years

Exclusion Criteria

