1. Children under the age of 21

Consent Procedures

Correction Officers staff will receive an information sheet at the beginning of the questionnaire explaining the study, confidentiality, and possible risks and benefits. Continuing on to the questionnaire will imply that the subject consents to take part to the study. The survey takes about 10 minutes. We will not be using a signed informed consent form so that this study can be anonymous in addition to being confidential.

Waiver of Documentation of Consent

We will not be collecting any identifiable information from survey participants (Correction Officers); the surveys will be anonymous. Our plan to use a "Participant Information Document" (rather than signed Informed Consent Form) will allow us to not collect name and signature.

Study Procedures

We will collect pre-Targeted Educational Campaign (TEC) and during-TEC (at 6 months and 12 months) survey data, which will be used to test engagement of Target C: changes in mean scores for behavioral capability, expectations, and self-efficacy, which are three key constructs from Social Cognitive Theory. The brief (10-minute) survey will assess knowledge and skills (behavioral capability), expectations, and

self-efficacy. It will be offered to any staff in the jail, regardless of whether they have received an in-person (e.g., in roll call) training, since the various types of TEC materials are hypothesized to influence behavior, expectations, and self-efficacy.

Assessment Instruments

Correction Officer Surveys: will measure three constructs from Social Cognitive Theory (behavioral capabilities (knowledge/skills), expectations, self-efficacy), as well as social distance stigma, while keeping the survey to approximately 10 minutes.

Risks/Discomforts/Inconveniences

We do not foresee any risks for Correction Officers. Their participation is completely voluntary and the information collected will be confidential and anonymous, and will not be disclosed outside of the research team.

Procedures for Minimizing Risks

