individual participants will only be released with their informed and written consent, except in unusual cases where withholding such information might pose a serious risk or danger to the participant or others. Publications and presentations will not report names, initials, or descriptors that could in any way violate confidentiality. These efforts to protect against potential risks are expected to be very effective, as they have been for our prior research.

Direct Benefits to Subjects

There may be no definite direct benefits to individual participants of the proposed study. Given the minimal risks and potential benefits of the proposed research to participants and the significant potential benefit of knowledge gained, there is no evidence that the risk-benefit ratio would suggest changes to the research plan at the present time.

Statistical Analysis Plan

The Targeted Educational Campaign (TEC) is designed to lead to referrals of detainees (previously not detected as having potential mental health concerns) to Correctional Health Services (CHS) by Correction Officers within 3 jails at NYC's Rikers Island. We expect that referral will occur via changes in scores on behavioral capability (knowledge/skills), expectations, and self-efficacy (among Correction Officers). Although this R34 feasibility study is meant to determine likely effect sizes rather than demonstrate statistical significance (which would be the goal of a subsequent, larger, multi-site study), using the data that we collect, we hypothesize that the number of referrals to CHS will be associated with: cumulative changes in Correction Officers' survey scores on behavioral capability, expectations, and self-efficacy.

Although survey participants who complete a short series of questions allow us to generate unique IDs that would be consistent across time, we expect that the number of surveys that matched from baseline to 6-months, from baseline to 12-months, and from 6-months to 12-months will be low. Therefore, rather than calculating changes in measurement scores as the primary outcome, each independent cohort (at each time point) will be considered to be a representative sample of the overall correction officer population over time, and we will use the measurement scores at 6-months as the primary outcome.

References

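### The SAP makes the 6-month scores primary without stating the comparison with baseline, and the documents describe nothing that fixes, records or adjusts for the mix of the three jails in each wave.

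*Combined protocol and SAP*

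**What the plan says.** The second paragraph of the Statistical Analysis Plan expects few surveys to match across time points. For that reason it does not use change in score as the primary outcome. In its place the SAP declares: "we will use the measurement scores at 6-months as the primary outcome". It supports this choice with an assumption about the samples, namely that "each independent cohort (at each time point) will be considered to be a representative sample of the overall correction officer population over time". It gives no comparator wave, contrast, model or covariate.

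Other sections bear on the same analysis:

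- **Study Procedures** says that pre-campaign and during-campaign surveys will test "changes in mean scores for behavioral capability, expectations, and self-efficacy". It also says of the survey: "It will be offered to any staff in the jail".
- **Description of Subject Population** says: "The study will need 540 completed surveys over the course of the three time points (180 surveys at each". It names three jails and gives no figure for any of them.
- **Recruitment Procedures** has officers approached at roll call, in the canteen, "or at a time/location agreed upon by the Department of Correction".
- **Recruitment Procedures** also has a contingency. If COVID-19 distancing rules keep researchers from going in "to survey the Officers at the 6 and 12-month follow-up time periods", supervisors hand out the form at roll call, and officers who wish to take part are told "they can put their completed survey in a container".
- **Assessment Instruments** lists three constructs plus social distance stigma, and **Procedures for Minimizing Risks** lists the questions behind the self-made code. Neither mentions jail.

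**The concern.** A mean score at 6 months is a level, not an effect. To say what the campaign did, it must be compared with another wave, and with few matched pairs that means comparing largely different groups of officers. The comparison is fair only if the groups are alike in everything that affects the score except the campaign.

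The SAP meets this need by declaring each wave representative. The collection method does not secure that: participation is voluntary, time and place are negotiable, and there is no target per jail. If the jails differ in average score and their shares differ between waves, the crude difference mixes the campaign effect with jail composition. More surveys would narrow the interval without moving its centre.

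The SAP says the study is meant to determine likely effect sizes for a later trial, so bias in an effect size bears directly on what the study is to deliver. Jail is also easy to note at collection. It could be hard to recover later if anonymous forms from several jails were pooled.

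**Working it through.** **The plan's own figure.** 3 waves × 180 surveys = 540, which reproduces the stated total. An equal split would be 180/3 = 60 per jail per wave; the documents state no split.

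**Assumptions, none of them in the documents.** SD = 1, so results are in SD units. Officers are independent, with 180 at baseline and 180 at 6 months. Each jail supplies 1/3 of baseline forms. One jail differs from the other two by d = 0.2, 0.3 or 0.5 SD. Its share at 6 months is w = 0.4, 0.5 or 0.6.

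**Precision of the crude difference.** SE = √(2/180) = 0.1054. The 95% half-width is 1.96 × 0.1054 = 0.207 SD.

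**Bias and coverage.** Bias b = d × (w − 1/3). Coverage = Φ(1.96 − b/SE) − Φ(−1.96 − b/SE).

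| Share at 6 months | Surveys moved | d = 0.2: bias, coverage | d = 0.3: bias, coverage | d = 0.5: bias, coverage |
|---|---|---|---|---|
| 0.4 | 12 | 0.013, 95% | 0.020, 95% | 0.033, 94% |
| 0.5 | 30 | 0.033, 94% | 0.050, 92% | 0.083, 88% |
| 0.6 | 48 | 0.053, 92% | 0.080, 88% | 0.133, 76% |

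For example, at d = 0.5 and w = 0.6: b = 0.5 × 0.2667 = 0.133, b/SE = 1.265, coverage = Φ(0.695) − Φ(−3.225) = 0.756. If d = 0 or w = 1/3, b = 0.

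**When coverage falls below 90%.** This needs b/SE above 0.652, that is b above 0.069 SD. The shift required is 0.069/d: about 62 surveys at d = 0.2, 41 at d = 0.3 and 25 at d = 0.5.

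**Cost of standardising.** With fixed jail weights W and jail shares p0 (baseline) and p1 (6 months), the SE ratio to the crude difference is √[(ΣW²/p0 + ΣW²/p1)/2].

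- Equal weights: 1.000 if balanced; 1.005, 1.027 and 1.072 at w = 0.4, 0.5 and 0.6.
- Illustrative headcount weights 0.5/0.3/0.2 with equal shares: 1.068. If the shares match the weights: 1.000.

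The same weights apply in both waves, so jail composition drops out of the standardised difference.

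**Choice of weights.** If the effect is 0.2 SD larger in a jail holding 60% of officers, headcount and equal weights differ by (0.6 − 1/3) × 0.2 = 0.053 SD.

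**If baseline jail is lost.** A correction that uses jail gaps seen at follow-up assumes the same campaign effect in every jail. If one jail's effect is 0.2 SD larger and its baseline share is 0.5, then even with that share known exactly, and equal weights as the target, the correction is wrong by 0.2 × (0.5 − 1/3) = 0.033 SD.

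**The case against.** Much can be said for the plan as written.

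- **The comparison can be inferred.** Study Procedures speaks of changes in mean scores before and during the campaign, and the SAP names 6 months. A reader might conclude that no comparison is intended; the documents do not support that. What stands is that the SAP never writes the contrast down.
- **Change scores are not abandoned.** They are set aside only as the primary outcome. The self-made code still allows matching, and the hypothesis linking referral counts to cumulative score changes remains. But the SAP itself expects few matches, and that hypothesis does not define a wave contrast.
- **Jail may be recorded.** A reader might infer that it is not. The form is not in the documents, and staff collecting surveys inside a named jail could know the site. Nor do the documents say that forms will be pooled. What can be said is that they describe no recording and no use of jail.
- **The sizes are assumed.** At a 0.2 SD gap, coverage stays at 92% even at a 0.6 share, and one jail would have to supply about 68% of the wave (1/3 + 62/180) before it fell below 90%. This objection stands in full: the documents give no evidence that jails differ or that their shares move.
- **The change in collection is conditional.** It applies only if distancing rules keep researchers out, so it cannot be treated as certain.
- **This is a feasibility study that does not aim at significance.** That is true, but estimating effect sizes is its stated aim, and composition bias affects an estimate whether or not it is tested.

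**Conclusion.** The point holds in a limited form, and the SAP should be amended. On the text alone, the SAP states no wave contrast, calls voluntary convenience samples representative, and has no plan for jail. Followed literally, it yields either a 6-month level with no effect estimate or a crude difference open to a shift in jail mix.

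The size of any bias is unknown. Over assumed gaps of 0.2-0.5 SD it runs from 0.03 to 0.08 SD if one jail's share goes from 1/3 to 0.5, and from 0.05 to 0.13 SD if it goes to 0.6, against a 95% half-width of 0.207 SD. Small shifts do little harm. The reading that the campaign estimate is known to be biased, or that its interval is known to fail, goes beyond the documents. Confidence is medium, because jail may already be on the form.

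**What to change.** 1. State the primary contrast in the SAP: the 6-month minus baseline difference in mean score, for each score.
2. Have the collector label each batch of forms with jail and collection route, and report counts by jail and wave. Officers are asked nothing new.
3. Estimate the difference from a model with wave, jail and wave-by-jail terms, standardised to one prespecified set of jail weights, and show the crude difference beside it. If baseline jail cannot be recovered, report a composition-corrected difference over a range of baseline jail shares, and state that it assumes the same campaign effect in each jail. The crude difference is a single observed number and does not vary with assumed shares.
4. Replace the claim of representativeness with inference to responding officers in these three jails. Note that self-selection remains. Note also that, if the COVID-19 contingency is used at follow-up, the effect of collection mode is confounded with wave and cannot be adjusted away.

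The cost is SAP wording, one or two batch labels, minor analysis work and a standard error about 0-7% larger. The weights need a deliberate choice, because equal and headcount weights answer slightly different questions. Jail and route also add a little detail to an anonymous dataset.

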Any risk of perceived coercion will be addressed by fully informing participants that their decision to participate is voluntary and will not be reported to anyone outside of the research team. We (or in the event that we cannot distribute the surveys due to social distancing, the Deputy Wardens and Captains) will explain that their decision will in no way impact their relationship with their employer or others. Risks to confidentiality also will be minimized. Participants' names and other potential identifiers will not be included in the dataset and each participant will be assigned a unique ID number. Surveys will be made anonymous by using a unique code created by the participant, as in [name] prior survey-based research. For example, on the front page of the survey, respondents will be asked:

- What is the first letter of your middle name?
- What is the first letter of the street you live on?
- What is the last digit of the year you were born?
- What is the last two digits of your Social Security Number?

Doing so will create a unique identification code for each participant (e.g., JB223, TF189) to ensure anonymity, while allowing us to match any participants who complete a later survey (at 6 months or 12 months).

Method to Protect Confidentiality

We will collect some identifiable information that will be used for the purpose of determining basic eligibility criteria, and we will carefully protect such information. All information collected will be confidential and will not be disclosed outside of the research team. We will keep all records private and confidential to the extent permitted by law.

All initial screenings and interviews will be conducted in the same private interview rooms/spaces used by Correctional Health Services staff for meetings and counseling sessions. Consent forms with participants' signatures will be securely stored in a locked file cabinet in a locked research office in a secure building.

Subjects' name and other potential identifiers will not be included in the notes or dataset, and each participant in the study will be assigned a unique ID number. The only link between identifying information and the unique ID number will be the paper consent forms. Information pertaining to

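### Expecting few matched surveys does not make the three survey waves independent; the officer code already collected should enter the between-wave analysis

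*Combined protocol and SAP*

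**What the plan says.** Description of Subject Population sets the target in surveys, 180 at each of three time points, and adds that "it is possible that some of Correction Officers will participate more than once, meaning less than 540 Officers total will participate". Procedures for Minimizing Risks has each respondent build a code from two initials and three digits, which is meant to preserve anonymity "while allowing us to match any participants who complete a later survey (at 6 months or 12 months".

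The Statistical Analysis Plan acknowledges these codes. It says "we expect that the number of surveys that matched from baseline to 6-months", and for the other two pairs of waves, will be low. From this it concludes that "each independent cohort (at each time point) will be considered to be a representative sample of the overall correction officer population over time", and that "we will use the measurement scores at 6-months as the primary outcome".

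Between-wave comparisons nevertheless stay in the plan. Study Procedures describes the test of Target C as "changes in mean scores for behavioral capability, expectations, and self-efficacy", and the Statistical Analysis Plan still relates referrals to cumulative score changes. It gives no rule for surveys that match between waves or repeat within one, no variance method and no sensitivity analysis.

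**The concern.** A low number of matches is a sound reason not to build the primary outcome on within-officer change, because too few pairs would carry it. Independence is a different matter: if some officers answer at two waves, the two wave means are correlated, however few those officers are. The code that would measure and handle this is collected but given no stated use in the analysis.

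The study exists to supply effect sizes for a larger trial. A single 6-month mean is not a campaign effect, so any effect size must come from a contrast between waves, and that contrast needs an error model that fits the sampling.

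A second gap lies within a wave. Surveys are collected in the canteen or at roll call and, under the COVID-19 contingency at 6 and 12 months, through an unattended container. No duplicate check is described, so one officer could count twice towards the same 180.

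**Working it through.** **The plan's own figure.** 3 × 180 = 540, as stated. The 180 itself cannot be derived, because no significance level, power, standard deviation (SD) or effect size is given.

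**Inputs.** From the documents: n = 180 per wave. Assumed, because the documents give no figures: f, the share of each wave also present in the other; ρ, the within-officer correlation between waves; k duplicate pairs within a wave, with correlation r. Results are in SD units. The plan states no variance formula, so the comparison is with the ordinary formula for independent samples.

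**Single-wave 6-month mean.** The standard error (SE) is 1/√180, and the 95% half-width is 1.96/√180 = 0.146. Neither f nor ρ enters, so overlap with other waves does not affect it.

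**Difference between two waves.** With fn officers in both waves, the covariance of the two means is fρ/n, so the variance of the difference is (2/n)(1 − fρ). Under independence the SE is √(2/180) = 0.105 and the half-width 0.207. Allowing for overlap:

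| f | ρ | 1 − fρ | true SE ÷ independence SE | independence interval too wide by | true half-width |
|---|---|---|---|---|---|
| 5% | 0.3 | 0.985 | 0.992 | 0.8% | 0.205 |
| 10% | 0.7 | 0.930 | 0.964 | 3.7% | 0.199 |
| 30% | 0.3 | 0.910 | 0.954 | 4.8% | 0.197 |
| 30% | 0.7 | 0.790 | 0.889 | 12.5% | 0.184 |

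The direction is conservative. In the four rows a nominal 5% test would run at 4.8%, 4.2%, 4.0% and 2.7%.

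**Duplicates within a wave.** The variance of the mean is (1/n)(1 + 2kr/n). With k = 9:
- r = 0.8: 1 + 2 × 9 × 0.8/180 = 1.08, so the true SE is √1.08 = 1.039 times the naive one.
- r = 0.9: the factor is 1.09, and the SE ratio is 1.044.

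Here the naive SE is too small, by about 4%.

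**Can the code carry the load?** It has 26 × 26 × 10 × 100 = 676,000 possible values. If all were equally likely, chance matches would number about (180 × 179/2)/676,000 = 0.02 within a wave and 180²/676,000 = 0.05 between two waves. If initials are uneven, with an assumed 12 effective letters each, there are 144,000 values and the figures are 0.11 and 0.23. False matches are therefore a small problem. Missed matches are likelier, since a street initial can change and items can be skipped.

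**The case against.** The approximation is disclosed, with its reason. The background section reports high correctional staff turnover, which fits low overlap. The primary outcome is a single wave, the error in between-wave contrasts is on the safe side, and the study disclaims significance testing. Duplicates within a wave are mentioned nowhere, and the code would expose them at data cleaning. The two SE errors also pull in opposite directions for a difference: with 10% overlap at ρ = 0.6, and 9 duplicate pairs at r = 0.8 in both waves, the variance factor is about 1.08 − 0.06 = 1.02. All of this stands, and it keeps the point small. It does not supply a rule for the surveys that do match. A low match count does not prove low overlap, and the cancellation depends on quantities that nobody has measured.

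A reader might infer more than the documents support:

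- **That the protocol expects repeat participation.** It says only that it is possible.
- **That the error bars of the primary outcome are wrong because waves overlap.** They are not. Only duplicates inside the 6-month wave could affect them.
- **That the follow-up means are wrong.** Overlap alone shifts no mean. A shift needs an effect of having answered before, or selective repeat participation, and the documents give no figure for either. With an assumed retest effect c the shift is f × c: 0.1 × 0.2 = 0.02 SD, or 0.27 of the SE of a wave mean, up to 0.3 × 0.3 = 0.09 SD, or 1.2 SE. The upper figure combines a high overlap with a high effect, and neither is documented.

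**Conclusion.** The step from few matches to independent cohorts does not follow, and the plan leaves unused the code that would replace the assumption. The consequence is modest. If overlap is as low as the sponsor expects (5 to 10% assumed, ρ 0.3 to 0.7), intervals for changes in mean score are about 1 to 4% too wide; the range of 5 to 13% requires 30% overlap. The understatement of about 4% in the SE of a wave mean is conditional on 9 duplicate pairs, which the documents neither mention nor prevent. This is a cheap improvement to the analysis, not a flaw that overturns the primary outcome. Whether each wave is representative is a separate question that this point does not address.

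**What to change.** In the Statistical Analysis Plan:

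1. Replace the independence assumption for between-wave contrasts with one model of all surveys, with the officer code as the cluster (GEE or a random intercept).
2. Within a wave, keep the first survey per code, and count the 180 after duplicates are removed.
3. Report the number of codes matched for each pair of waves and the number repeated within each wave.
4. Optionally, show the 6- and 12-month means with and without matched earlier respondents. Label this as descriptive only: those respondents have been in post since an earlier wave, so a difference could reflect retest, tenure or exposure to the campaign.

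The cost is a few sentences and a few lines of code, since the code is already collected. A few surveys are dropped and may need replacing to reach 180. Some repeats will be missed when a code changes. If overlap is as low as expected the results will hardly move, and the reported match counts will give readers a basis for judging that.
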